7 OVERALL DESIGN AND PLAN OF THE TRIAL

7.1 Trial Overview

This is an uncontrolled, single centre phase II trial. Enrolled HVs (n=10) will undergo Gd-enhanced MRE after oral intake of Lumentin® 44.

Interested HVs will be identified primarily among medical students at the medical hospitals at Malmö and Lund. Posters will be placed at the departments and invitation letters will be handed out.

The HVs interested in participating will be invited to attend a pre-screening visit where their suitability based on age and health status will be assessed. Fifteen HVs who fulfil the pre-screening criteria and are interested in participating will be asked to attend a screening visit at the clinic and if eligible for the trial they will then visit the clinic for the MRE assessment within 1-2 weeks.

Only the initial 10 of the eligible HVs will be asked to come for the MRE examination and the remaining eligible subjects will be asked to stand by in case any of the 10 subjects are unable to come or cannot undergo the examination.

HVs will be asked to fast for 6 hours prior to the examination on the day of the MRE examination. Small amount of clear liquid is allowed up to 2 decilitres. Prior to MRE, Lumentin® 44 will be provided to them in volumes of up to 1,500 mL and at least 1,100 mL of Lumentin® 44 must be drunk. The subjects will be asked to drink the solutions of oral contrast agent within 45 minutes to 1 hour.

Subjects not able to drink at least 1.1 L of Lumentin® 44 will be withdrawn from the trial.

Prior to the intake of Lumentin® 44, an IV antecubital cannula will be placed and used for blood sampling and administration of gadolinium (Gd) contrast agent during the MRE assessment.

7.2 Outcomes

7.2.1 Primary Outcome

Visual evaluation of the MRE images from each trial subject with respect to motility, artefacts, mucosal evaluation and overall diagnostic impression.

7.2.2 Secondary Outcomes

- Concentration of plasma electrolytes including, potassium, sodium, phosphate, and calcium, as well as ionized calcium in blood samples taken at T0h, T1h, T2h, T4h, T6h, T8h, and T24h.
- Bowel filling properties (extension and distension) in each of 5 selected sub-segments of the small bowel.
- Any treatment emergent adverse events (TEAEs) and treatment emergent adverse drug reactions (TEADRs).

7.3 Justification of the Trial Design

7.3.1 Justification for Design and Parameters

Lumentin® 44 is currently being developed to be used as a small bowel filling contrast agent when CT examination is performed. Two clinical trials have so far been performed and a phase 3 trial is planned to start 2023.

Most radiology departments perform both CT and MRE examinations and it is advantageous and convenient for them to be able to provide the same oral contrast agent for both procedures. Lumentin® 44 is food based with Generally Recognized as Safe (GRAS) excipients and has in the previous clinical trial been accepted and tolerated well with only mild to moderate AEs reported. In the LUM-001 trial in subjects referred for abdominal CT-examination that evaluated the CT image quality and diagnostic feasibility of Lumentin® 44 in comparison with diluted Omnipaque and Movprep, the most common TEAEs in the Lumentin® 44 arm, were flatulence (4 subjects, 22%) and nausea (2 subjects, 11%). In the LUM-002 clinical trial in patients with small bowel Crohn's disease that evaluated Lumentin® 44 as contrast agent in CT-enterography as compared to MRE, the most common (occurring in ≥ 2 subjects) TEAEs, in the Lumentin® 44 arm, were diarrhoea (10 subjects, 18%), nausea (3 subjects, 5%), and flatulence (2 subjects, 4%).

To be able to use Lumentin® 44 in MRE, the diagnostic quality cannot be inferior to the standard oral regimen. Therefore, the trial selected pivotal parameters in reading MRE as primary endpoints.

As the air in Lumentin may degrade the image quality in MRI in the interface to soft tissue the most relevant parameters were chosen. In motility sequences the moving small intestine filled with air may aggravate the problem and the other parameters where the small intestine should remain still it is most relevant to scrutinize the structures, e.g., mucosal folds, in the interface between air and soft tissues.

It is important for the quality of the MRE images that the small bowel is adequately filled with the contrast agent. The clinical endpoint measuring filling properties is therefore included. Extension is the measurement of how far down in the small bowel the contrast agent has reached, and the distension parameter measures the how distended (widened) the small bowel is.

Palatability of the contrast agent is an important factor for the subject's acceptance and ability to drink it. The subjects are therefore asked to evaluate features describing how they experience drinking the Lumentin® 44 foam.

The choice of not including a comparator and expose the HV to another contrast agent have been made based on that the aim of the trial is to investigate the general quality of the MR images when using Lumentin® 44, and that both the investigational MRE examination and the drug Lumentin® 44 are safe to use. From a medical, empirical, perspective it is not considered necessary to include more than 10 subjects to generate data sufficient for showing PoC. The sample size is not determined on any mathematical grounds as this is a PoC trial.

HVs to be enrolled in the trial must be able to undergo an MRE examination and should not have any known egg allergy.

7.3.2 Justification for Route and Dosage

A total of 73 subjects in previous clinical trials (LUM-001 and LUM-002) were asked to drink between 0.75 -1.5 L foam and the average amount drunk was 1026 mL of Lumentin® 44 foam. The amount of contrast agent that a subject can drink varies between subjects depending on e.g., age, weight, gender and medical condition. It is therefore necessary to define the recommended dose within a range.

This trial will recruit predominantly young HVs, and electrolyte levels will be investigated. The range is therefore narrower and the lower limit in the range is also higher than in previous trials. The lower limit in the dose range is set to 1.1 L. The recommended dose will be 1.2 L with the allowed upper range set to 1.5 L.

Sponsor: Lument AB

Clinical Trial Protocol

Protocol: LUMRIS-001, version 2.0 Final

CONFIDENTIAL

The route of administration is according to standard practice for an oral contrast agent.

8 TRIAL POPULATION

The trial population will consist of healthy volunteers.

The subjects must be able to provide written informed consent and meet all the inclusion criteria and none of the exclusion criteria.

8.1 Inclusion Criteria

Subjects will be entered into this trial only if they meet all the following criteria:

1. Healthy volunteers of either gender at least 18 years at the time of signing the informed consent.
2. Females must either present a negative pregnancy test or be surgically sterile (hysterectomy or tubal ligation) or postmenopausal (i.e., experienced 12 consecutive months without menstruation).
3. Following verbal and written information about the trial, the subject must provide signed and dated informed consent before any trial related activity is carried out.

8.2 Exclusion Criteria

Subjects will not be enrolled if they meet any of the following criteria:

1. GFR below 60 ml/min/1.73 sqm body surface. All subjects will have a plasma creatinine taken at screening for calculation of eGFR.
2. History of drug related reaction to gadolinium contrast agents.
3. Have had gadolinium injection during the last 4 weeks.
4. Claustrophobia not coping with MRE examination.
5. Metal objects and medical devices in the body not judged by the investigator to be compatible with MRE.
6. Hypersensitivity to Buscopan® (Butylhyoscopin).
7. Having swallowing difficulties.
8. Known allergy to egg albumen.
9. Known sensitivity to any of the components of the investigational product.
10. Clinical suspicion of ongoing disease by the investigator.
11. Being, in the opinion of the investigator, unlikely to comply with the clinical trial protocol.
12. Previously randomized to participate in this trial.
13. Participating in or having participated in another clinical trial within the last 4 weeks.

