5.4 Risk-Benefit Assessment

EWP is widely used as a food ingredient. All excipients in Lumentin® 44, are of pharmacopoeia quality (buffer and stabiliser). The flavour complies with regulations concerning flavouring in food and food additives.

The side effects reported by subjects drinking up to 1.2 L of the Lumentin® 44 formulation in previously conducted trials indicate that Lumentin® 44 was well tolerated with only mild to moderate AEs reported.

Allergic reactions towards egg protein cannot be excluded and patients with a known sensitivity towards egg should not be exposed to Lumentin® 44.

Ingestion of a large volume of foam in a short time may have an impact on the resorption pattern of concomitant medications. Intake of other medications, which are absorbed in the small bowel, and having a narrow therapeutic window, should be avoided within a period of 4 hours before and until 1 hour after administration of Lumentin® 44.

Potential side effects associated with intravenous (IV) catheterization include insertion site pain, phlebitis, hematoma formation and infusate extravasation. Mechanical issues such catheter obstruction/occlusion and dislodgement may occur. The hospital sites staff is very familiar and alert to signs and symptoms of such complications, and preventive measures are in place, as well as intervention procedures for if/ when complications do occur. The IV catheter will remain in place for the duration of the visit 2 (day of MRE procedure), until collection of 8h blood sample.

The proposed Phase II study will enrol only HVs and as such no direct benefit is expected for the trial subjects.

Risks associated with Covid-19

Considering that the subjects in the trial will be HVs, the risk of contracting COVID-19, as part of the trial procedures is considered low.

All subject visits to the hospital will occur in facilities which are not used for patients with COVID-19. Procedures to prevent COVID-19 infection, as recommended by the Swedish "folkhälsomyndigheten", will be followed.

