10 PROHIBITED PREVIOUS AND CONCOMITANT MEDICATION

10.1 Concomitant Medication

Any medication the subject takes other than the investigational product (prescribed and over-the-counter-drugs) is considered a concomitant medication. All concomitant medications must be recorded in the CRF. The following information must be recorded in the CRF for each concomitant medication: generic name, route of administration, start date, stop date, dosage, and indication. Any changes in the dosage or regimen of a concomitant treatment must be recorded in the CRF.

At visit 1, subjects will be asked what medications they have taken during the last 2 weeks before visit 1. Concomitant medications will be recorded at each visit and during telephone interviews, if applicable.

All subjects will receive:

1. An intravenous injection of Buscopan 40 mg. The dose given and batch number of Buscopan 40 mg will be noted in the CRF
2. An intravenous injection of the Gd contrast agent (Clariscan®, 0.5M) during the MRE-examination at a dose of 0.1 mmol/kg b.w. The volume given is typically 10 – 20 ml. The dose given and batch number of the Clariscan® 0.5M will be noted in the CRF.

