10.4 Precautions/overdose

Risks associated with intake of oral contrast agents include dysphagia with aspiration and secondary pneumonia. Although this trial intends to enrol only healthy volunteers and subjects with acute problems are excluded, a pre-emergency small bowel status might be aggravated to an established ileus by ingesting a large volume. Oral contrast agents should not be given to unconscious subjects, to those with swallowing disorders, or an acute abdomen problem.

Known sensitivity or allergy to contrast agent ingredients are exclusion criteria in clinical studies. However, unknown sensitivities or allergies might cause reactions that may need to be medically treated.

Intravenously administered Gd may cause allergic reaction of various severity from a mild rash to intensive care unit treatment. This is especially true for those with allergic reactions to a contrast agent earlier in life. Allergic reaction may be triggered in those with asthmatic bronchitis and treated with beta-blockers. Routines for handling these cases are well known to the staff which is regularly trained in dealing with emergency cases. Equipment for emergency care treatment is available at the clinic and the clinic is located in close proximity to the hospital emergency care department. Neither Buscopan nor Gd should be administered to patients with severe kidney failure.

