11.2.7 MRE examination

Preparation before MRE: Subjects will be fasting (2 decilitres of clear water is allowed) for at least six hours prior to the MRE procedure.

The MRE-examination will take approximately 40 minutes. The MR-examination will not be performed if the subject has not been able to drink at least 1.1 L of Lumentin® 44.

Broadly, MRE is a scanning technique for creating detailed images of parts of the human body, using a strong magnetic field and radio waves. It is based on the magnetisation properties of atomic nuclei. A powerful, uniform, external magnetic field is employed to align the protons that are normally randomly oriented within the water nuclei of the body part examined. This alignment (or magnetisation) is disrupted by introduction of an

external Radio Frequency (RF) wave energy. The nuclei return to their resting alignment through various relaxation processes and in doing so emit RF energy. Tissues are characterised by two different relaxation times, of which T1, the longitudinal relaxation time, determines the rate at which excited protons return to equilibrium. It is a measure of the time taken for spinning protons to realign with the external magnetic field. The contrast and brightness of the image are predominately determined by T1 properties of tissue.

During an MRE-examination, the subject will be asked to lie prone on a movable table that will slide into a doughnut-shaped, deep opening and centred for scanning the small bowel. As part of the procedure a strong magnetic field will be generated around the subject, and pulsating radio waves will be directed at the body. Because of loud thumping and tapping noises during the scan the subject will be given headphones to listen to music or earplugs to help block the sound. The subject will be able to communicate with the technician who gives instructions during the test. The contrast agent Clariscan® (0.1 mmol/kg) and the muscle relaxant Buscopan® (40 mg) (to reduce bowel motility) will be administered IV. Clariscan and Buscopan can be replaced with comparable product according to the standardised procedures at the clinic. The specific details of the MRE-system used will be noted in the CRF.

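### Exclusion 2 covers earlier reactions to gadolinium agents only, while sections 10.4 and 12.6 tie the gadolinium risk to an earlier allergic reaction to any contrast agent

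*Combined protocol and SAP*

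**What the plan says.** **Eligibility.** Section 8.2 and the synopsis carry the same exclusion 2: "History of drug related reaction to gadolinium contrast agents". Exclusion 6 covers hypersensitivity to Buscopan and gives its substance, butylhyoscopin. Criteria 2 and 6 are both on the shortened list checked at pre-screening (Visit 1, section 11.1.1).

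**Stated risk.** Section 10.4, repeated almost word for word in 12.6, warns that intravenous gadolinium can provoke allergic reactions ranging from a mild rash to ones needing intensive care. It then says "This is especially true for those with allergic reactions to a contrast agent earlier in life" and "Allergic reaction may be triggered in those with asthmatic bronchitis and treated with beta-blockers".

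**Exposure.** Section 10.1 lists what every subject will receive: "An intravenous injection of Buscopan 40 mg", and Clariscan, a gadolinium agent. Section 11.2.7 adds that "Clariscan and Buscopan can be replaced with comparable product according to the standardised procedures at the clinic".

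**Justification.** Section 5.4 states that "no direct benefit is expected for the trial subjects". The risks it covers are egg allergy, altered absorption of other medicines, the intravenous catheter and COVID-19. It does not mention reactions to gadolinium or to the spasmolytic.

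**The concern.** The protocol names a history that raises the risk of a gadolinium reaction, then screens for only part of it. Section 10.4 speaks of contrast agents in general, and exclusion 2 speaks of one class. Someone who reacted to, say, an agent given for a CT examination falls in the space between the two.

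The subjects are healthy volunteers who receive gadolinium because they are in the trial. If the protocol's own account of the risk is right, people in that space face a raised chance of a reaction with nothing to gain personally, and no part of the plan records a decision to accept this. The issue is one of subject safety and internal consistency. It does not affect how the image-quality scores are analysed.

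**Working it through.** No arithmetic applies. Exclusion 2 has no stated figure behind it, and section 13.2 says the sample size of 10 has no mathematical basis. The check sets each risk in 10.4, and each substitution in 11.2.7, against all the criteria and medication rules.

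1. **Earlier allergic reaction to a contrast agent other than gadolinium** (10.4, 12.6).
   - Exclusion 2 does not apply, because it is limited to the gadolinium class.
   - Exclusion 9 concerns components of the investigational product, so it does not apply.
   - Exclusion 10 concerns suspected ongoing disease, and a past reaction is not that.
   - Inclusion 1 requires a healthy volunteer, and such a person can be entirely healthy.
   - Medical history is documented for the last 2 years before screening (11.2.2), whereas 10.4 speaks of a whole lifetime. An older reaction may not surface, and if it did, no criterion would act on it.
   - Result: no exclusion is met. The gap is confirmed.

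2. **Asthmatic bronchitis and beta-blocker treatment** (10.4, 12.6).
   - No criterion names either.
   - Inclusion 1 and exclusion 10 both bear on asthma, by investigator judgement.
   - Section 10.2 bars all medication from 4 hours before to 1 hour after intake, then allows only contraceptives and occasional painkillers. Regular beta-blocker use conflicts with that.
   - Under 8.3.2, however, use of prohibited medication is a reason for which a subject may be withdrawn. It is neither mandatory nor an eligibility criterion.
   - Inclusion 1 sets no upper age limit ("Healthy volunteers of either gender at least 18 years at the time of signing the informed consent"), and section 7.1 recruits primarily, not only, among medical students.
   - Result: addressed, but only indirectly.

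3. **Replacement of Buscopan** (11.2.7).
   - Section 10.1 names Buscopan with no alternative, while 11.2.7 allows one without defining what is comparable.
   - Exclusion 6 names butylhyoscopin, so another product of that substance is covered. A different substance is not.
   - Result: a mismatch between 8.2, 10.1 and 11.2.7, whose extent depends on an undefined term.

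4. **Replacement of Clariscan** (11.2.7). Exclusion 2 covers gadolinium agents as a class, so a different gadolinium agent is within it. Result: no gap.

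5. **Severe kidney failure** (10.4). Exclusion 1 removes anyone with a GFR below 60 ml/min/1.73 sqm. Result: no gap.

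Item 5 is a useful comparison: there the protocol turned a risk named in 10.4 into a criterion. For item 1 it did so only in part.

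**The case against.** The best reply is that a warning is not a prohibition. Section 10.4 uses prohibitive wording for unconscious subjects, swallowing disorders, an acute abdomen and severe kidney failure. For an earlier contrast reaction it only describes a higher risk, followed by mitigation: trained staff, emergency equipment and a nearby emergency department. On that view the sponsor has chosen to manage the risk, and wanting an exclusion is a preference.

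Part of this stands. The documents do not oblige the sponsor to exclude the group. But mitigation governs what happens after a reaction, not who is exposed. Exclusion 2 also shows that the sponsor did treat a previous reaction as a matter of eligibility, only more narrowly than 10.4 describes the risk. If the narrower scope is intended, section 5.4 is the place to say so, and it is silent.

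A reader might infer four stronger things that the documents do not support:

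- **That volunteers with asthma who take beta-blockers are simply eligible.** Inclusion 1, exclusion 10 and section 10.2 all restrict them, though partly by judgement.
- **That people hypersensitive to a substitute spasmolytic are one of the protocol's own risk groups.** Section 10.4's only caution about Buscopan concerns severe kidney failure, which exclusion 1 covers.
- **That wider criteria would make an allergic reaction easier to attribute.** Every subject receives both the egg-protein foam and gadolinium, so the difficulty remains whoever is enrolled. Section 12.2.2 already offers a causality category for events that another drug could explain.
- **That a known share of volunteers is affected.** The documents give no prevalence for any of these histories.

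**Conclusion.** The point holds for the first group. A healthy volunteer with an earlier allergic reaction to a non-gadolinium contrast agent is at raised risk by the protocol's own account, meets no exclusion and may be missed by the 2-year history. That person would be given gadolinium without a stated justification.

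The exposure is universal, since all 10 subjects receive gadolinium. The number of candidates with such a history cannot be estimated from the documents and could be zero. The conclusion rests on reading the contrast agent in 10.4 in its ordinary, unrestricted sense. If the sponsor meant gadolinium agents only, the mismatch is one of wording, and 10.4 and 12.6 are the places to correct.

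The other two points are secondary. The asthma/beta-blocker group is handled by inference, and exclusion 6 does not follow the substitution that 11.2.7 permits.

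**What to change.** - Reconcile exclusion 2 in section 8.2 and the synopsis, and the Visit 1 check of that criterion, with the history named in 10.4 and 12.6. Alternatively, state in 5.4 why volunteers with that history are admitted.
- Reconcile 10.4 and 12.6 with 8.2 and 10.2 for the asthma/beta-blocker group, so that its status does not have to be inferred from other rules.
- Reconcile exclusion 6 and section 10.1 with the substitution allowed in 11.2.7, and say there what counts as comparable.

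Which way each is resolved is a clinical decision for the sponsor. The work is a few lines in the criteria, the synopsis and the pre-screening checklist, or a short paragraph in 5.4. If the criteria are widened, slightly fewer volunteers may qualify, by a number the documents do not give. Criterion 2 is already checked at Visit 1, before the 15 volunteers are invited to screening. A candidate lost there can be replaced from the pre-screening pool without using up the five on standby (15 − 10 = 5), provided enough volunteers come forward.

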8.3 Subject Withdrawal and Replacement

8.3.1 *Withdrawal from Trial Therapy*

Subjects must be withdrawn if the intake of the contrast agent has to be stopped, please see section 9.2 Dosage and Administration.

8.3.2 *Withdrawal from Study*

Subjects may withdraw from the trial at any time and for any reason without prejudice to his or her future medical care.

Subjects must be withdrawn under the following circumstances:

- The subject withdraws consent
- Subjects who have not fasted (clear water allowed) for at least six hours prior to the intake of the contrast agent
- The subject is unable to drink at least 1.1 L of Lumentin® 44
- The subject is unable to complete the MRE examination, due to e.g., claustrophobia.
- Violation of eligibility criteria

Subjects withdrawn due to the above circumstances will be replaced by one of the five remaining eligible HV subjects on standby after screening.

Subjects may be required to withdraw after discussion with the Sponsor and/or Investigator for the following reasons:

- AEs
- Use of prohibited medication (see Section 10)
- At the discretion of the Investigator

In all cases, the reason(s) for withdrawal must be recorded on the Case Report Form (CRF). If a subject is prematurely withdrawn from the trial for any reason, the Investigator must make every effort to perform the evaluations described for the Early Termination Visit (see Section **Fel! Hittar inte referenskälla.**).

If a subject has withdrawn informed consent and still agrees to attend the Early Termination Visit, this will be documented on the CRF.

For subjects who are withdrawn after they receive the trial drug, the Early Termination page will be completed in the CRF.

HVs withdrawn prior or during the MRE examination (i.e., no evaluable MRE scan has been generated) will be replaced by a new HV. HVs withdrawn after the completion of MRE examination and NOT fulfilling the mandatory criteria for withdrawal listed above will not be replaced.

